12.4. Potential Analytic Concerns in Primary Efficacy Analyses

Lost to Follow-up: We designed this study to recruit 278 total patients so that 200 are available at the end of the study. Thus, we will need to consider how to analyze data from the 78 patients who may drop out. To examine whether the missing data are either missing completely at random or missing at random, we will compare the baseline characteristics of those who drop out and those who complete the trial. If there is no evidence of informative missing data, analyses will be done using the repeated measures ANCOVA with a mixed models approach (PROC MIXED in SAS). However, if there is evidence that the missing data are informative and treatment-related (e.g. if there are fewer dropouts in the statin group or if missingness is related to other medical outcomes that are strongly associated with the outcome of interest) and not MAR, then we will use more sophisticated statistical methods.⁷⁸⁻⁸⁰ One possible approach is to model the probability of dropping-out for each participant conditional on their baseline characteristics and treatment assignment. These probabilities would then be used to stratify participants (both completers and drop-outs) before making treatment comparisons. Thus each stratum would contain participants with similar predicted probabilities of trial completion (although only a subset would be completers). The final treatment effect estimates could be made using the completers with weights assigned to them based on the ratio of drop-outs to completers within each stratum. This approach and other methods for handling missing data have been previously described by [name].⁷⁸⁻⁸⁰

12.5. Secondary Analyses: Once the primary efficacy analysis is completed, secondary efficacy variables will be examined to provide insight into mechanisms by which statins may influence LVEF. These include: LVESV and strain (reflective of LV contractility), LVEDV (reflective of LV pre-load), PWV and aortic wall thickness (reflective of LV after-load), and LVECV (a measure of myocellular replacement fibrosis). In addition, we will measure a series of subclinical biomarkers, including serum lipids (LDL, TC, HDL), glucose, serum troponin I, CRP, IL-6, TNF- α , renin, and aldosterone at the 6- and 24-27 month endpoints. For each, we will fit ANCOVA models that will examine the 24-27 month endpoints adjusted for baseline assessments, followed by ANCOVA models that also include patient-level characteristics. Next, we will fit repeated measures ANCOVA models that incorporate intermediate (6-month) time point assessments. This approach will be repeated for the cognitive and patient reported outcomes. The latter analyses will also include data for the 12 and 18 months follow-ups.

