5.2. Atorvastatin/Placebo Administration

Patients will be 1:1 randomized to receive the study agent, (one 40 mg atorvastatin tablet daily by mouth for at least 24 months but no longer than 27 months) or a placebo (one tablet daily by mouth for at least 24 months but no longer than 27 months). The study agent or placebo should be started within 48 hours (2 days) prior to first chemotherapy treatment. The patient must receive 2 doses prior to first chemotherapy treatment. When possible those 2 doses may be given at least 12 hours apart. If necessary, due to time constraints, the patient may be given two tablets at the same time at least 90 minutes prior to first chemotherapy treatment.⁹⁸

Either agent will be taken once any time of day, with or without food, 7 days per week, on an outpatient basis, for a total of at least 24 months but no longer than 27 months. The atorvastatin pills and matching placebo pills used for this study will be provided free of charge to the patient.

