After primary efficacy analyses, additional analyses of the primary hypotheses will be done to assess relationships between treatment and outcome. We will fit ANCOVA models that consider the 24-27 month LVEF measure as the outcome, the baseline LVEF measure as a covariate, and other patient-level characteristics (e.g. age, cancer type, stage, and race) in order to control for other baseline covariates possibly related to LVEF in the model. Interactions between the treatment and covariates will be examined to determine whether the treatment effect is consistent across subgroups (e.g., black/white race by treatment interaction). Finally, we will conduct a repeated measures ANCOVA model that incorporates the intermediate (6-month) LVEF measurement into the model. We anticipate examining different covariance structures. Past experience suggests that a compound symmetry structure is usually appropriate; we will also examine whether an unstructured covariance is needed. We will fit these models using a mixed models approach, where the individual patient will be treated as a random effect in the model and the treatment indicator as patient characteristics (and baseline LVEF) will be considered as fixed effects. A mixed models approach for modeling the longitudinal data will allow for appropriate inference to be made in the presence of missing data (i.e., patient drop-outs) if the missing data are missing at random (MAR). Below, we describe methods to address MAR assumptions. Diagnostics and residual plots will be reviewed to ensure that all assumptions are met. If not, transformations of the outcome data will be considered, where the order of the priority in choosing a transformation will be to satisfy the (1) linearity assumption, (2) homogeneity assumption (homoscedasticity), and (3) normality assumption.

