In the above, r^2 is the percent of the variance of the follow-up outcome explained by the baseline measurement (LVEF), $Z_{1-\alpha/2}$ is the value from the standard normal distribution corresponding to the alpha level chosen (1.96, which corresponds to alpha=0.05 [two sided]), $Z_{1-\beta}$ is the value from the standard normal distribution that corresponds to the power chosen for the study (here 80% and 90%), and $n=100$ corresponds to the total number of patients studied for the statin group. We chose this sample size (100 per group) for power calculations to allow for up to 78 patients out of the 278 accrued to potentially drop-out. Note that this will somewhat conservative for the mixed models as those with partial data will also provide information. Based on preliminary data examining LVEF levels in comparable patients measured over a 6-month period we found that the standard deviation was approximately 7.7 and the correlation between baseline and 6-months was 0.5. Since we do not know what the correlation will be after 2 years, Table 5 depicts detectable differences for different correlations and power values. In addition, we show detectable differences for key secondary variables for which we have preliminary data (LVEDV, LVESV, and PWV).

Thus, for example, we have 80% power to detect a difference of 2.6% in LVEF between groups if the correlation between the baseline and 24-month LVEF is 0.5. In preliminary observational data, we saw a difference in LVEF between statin users vs. those who were not of 2.5% at 6 months. Thus, effect sizes of the magnitude in Table 5 are plausible and clinically meaningful. 2-6 ml increases in LVESV, or 3-5% drops in LVEF (from a normal resting LVEF) have been associated with adverse CV prognoses in a recent large trial of patients with HF and a preserved resting LVEF.⁸¹ In 483 hypertensive patients aged 50±13 years, aortic PWV measures of 11 m/s were associated with odds ratio of 2.14 for cardiac events ($p<0.0001$).⁸² Other studies that have initiated generic therapies such as ACE inhibitors or beta blockers with antioxidant properties have shown a reduced occurrence of CV events in cancer survivors.⁸³ Importantly however, it remains to be seen whether early initiation of statin therapy reduces the onset of subclinical CV disease in patients with breast cancer or lymphoma.

Outcome	Estimated SD	80% Power			90% Power		
		Correlation between baseline and 2-yr measure					
		0.4	0.5	0.6	0.4	0.5	0.6

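### The one drop-out model described in section 12.4 uses only baseline data and arm, so it leaves bias from drop-out tied to later events and omits the 6-month LVEF

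*Combined protocol and SAP*

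**What the plan says.** Section 12.4 (Potential Analytic Concerns in Primary Efficacy Analyses) expects 78 of 278 patients to drop out. It sets out two routes.

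- **No evidence of informative missingness.** The analysis is the repeated measures mixed model. Section 12.3 describes this as a model that "incorporates the intermediate (6-month) LVEF measurement into the model".
- **Missingness appears informative, treatment-related and not missing at random (MAR).** More elaborate methods follow. Two examples of the trigger are given: fewer drop-outs on statin, or "if missingness is related to other medical outcomes that are strongly associated with the outcome of interest".

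For the second route the section spells out one method, worded as a possibility and not a commitment. It is to "model the probability of dropping-out for each participant conditional on their baseline characteristics and treatment assignment", stratify everyone on that probability, and weight the completers within each stratum by the ratio of drop-outs to completers. No post-baseline variable is named. Other methods are mentioned by citation only. The check that decides between the routes compares baseline characteristics of drop-outs and completers.

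**The concern.** Weighting on baseline and arm is valid only if drop-out is random given baseline and arm. The mixed model needs less: drop-out must be random given baseline, arm and the observed 6-month LVEF. So when MAR is in doubt, the described fallback moves to a stronger assumption and uses less data. It also leaves unused the 6-month scans of patients who later drop out.

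Suppose patients whose LVEF has fallen by month 6 leave more often, and more so on placebo. The placebo completers then look too healthy and the statin effect is understated. The variables that could correct this are already collected: the 6-month MRI, toxicity, withdrawal from study drug, and start of an open-label statin (sections 7.7, 7.9 and 11.1).

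**Working it through.** **1. The plan's own figure.** Section 12.6 gives the inputs: "we found that the standard deviation was approximately 7.7 and the correlation between baseline and 6-months was 0.5"; "We chose this sample size (100 per group) for power calculations"; two-sided alpha 0.05. Allocation is 1:1 (section 5.2).

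Detectable difference = SD × √(2(1 − r²)) × (1.96 + 0.84) / √n = 7.7 × √1.5 × 2.80 / 10 = 2.64.

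This reproduces the statement that "we have 80% power to detect a difference of 2.6% in LVEF between groups if the correlation between the baseline and 24-month LVEF is 0.5". Enrolment also reproduces: 200 / 0.72 = 278. The design standard error of the treatment difference is 7.7 × √0.75 × √(2/100) = 0.94. The plan states no figure for drop-out bias.

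**2. Baseline-only weights against weights with the 6-month LVEF.** The check was a large simulation with 1,000,000 patients per scenario (simulation error about 0.02).

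- From the plan: SD 7.7; baseline correlation 0.5 with later LVEF; true effect 2.64.
- Assumed, because the documents give no values: 6-to-24-month correlation 0.6 or 0.8; drop-out after month 6 of 33% on placebo and 23% on statin; log-odds of drop-out linear in 6-month LVEF change.
- Weights: inverse of the estimated retention probability. The baseline-only model has arm, baseline LVEF and their interaction.

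| Drop-out slope per LVEF point | Correlation | Completer ANCOVA | Baseline + arm weights | 6-month LVEF added |
|---|---|---|---|---|
| 0.20 placebo, 0.05 statin | 0.6 | 1.87 | 1.83 | 2.64 |
| 0.20 placebo, 0.05 statin | 0.8 | 1.45 | 1.38 | 2.66 |
| 0.15 in both arms | 0.6 | 2.42 | 2.41 | 2.66 |
| 0.15 in both arms | 0.8 | 2.27 | 2.26 | 2.65 |

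A separate run that included the plan's stratified weights gave 1.37 to 2.40 for baseline-only weighting and 1.43 to 2.40 for unweighted ANCOVA. With equal slopes and equal drop-out rates in the two arms, no method is biased.

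**3. Allowing another prognostic baseline variable.** In step 2 the only baseline predictor is LVEF, which ANCOVA already adjusts for, so the weights had little to add. A second simulation (400,000 patients per scenario, 28% drop-out overall) allowed a further baseline covariate correlated 0.4 with later LVEF. It used ten strata and weights of (drop-outs + completers) / completers. Entries are bias against 2.64. Slopes are log-odds per SD.

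| Drop-out driven by | Completer ANCOVA | Baseline + arm weights | 6-month LVEF added |
|---|---|---|---|
| A: 6-month LVEF, placebo only, slope 1.5, correlation 0.7, no extra covariate | −1.22 | −1.26 | −0.13 |
| B: as A, with extra covariate | −1.21 | −0.90 | −0.19 |
| E: as B, slope 0.75 | −0.65 | −0.45 | −0.06 |
| F: as B, correlation 0.5 | −0.66 | −0.29 | −0.08 |
| C: as B, slope 1.0 in both arms | −0.13 | −0.11 | −0.03 |
| D: as B, but driven by the unseen 24-month LVEF | −2.02 | −1.74 | −1.43 |

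Share of bias removed by baseline + arm weights:

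- A: none
- B: (1.21 − 0.90)/1.21 = 26%
- E: (0.65 − 0.45)/0.65 = 31%
- F: (0.66 − 0.29)/0.66 = 56%
- C: (0.13 − 0.11)/0.13 = 15%

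Adding the 6-month LVEF removes 77% to 91% in A, B, C, E and F. A MAR regression model using the 6-month LVEF has bias between −0.01 and +0.03 in those five. In D it does no better than the 6-month weights (−1.43).

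**The case against.** **Baseline weighting might be said to remove none of this bias.** The documents do not support that. Section 12.4 refers to baseline characteristics in general, and section 12.3 names age, cancer type, stage and race as possible covariates. If any of these predict later LVEF, part of the bias goes, as step 3 shows. The result of none is a limiting case. The other trigger, fewer drop-outs on statin, is also one that a model including arm addresses in part.

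**The plan might be read as committed to this method, and as discarding the 6-month LVEF.** Neither follows. The wording is permissive, and one of the works cited for other methods is, by its title, about multiple imputation. Section 12.3 separately commits to the 6-month mixed model, whichever route section 12.4 takes. What stands is that the only method spelled out is weaker than the model it would replace.

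**The sizes rest on assumptions.** This is correct. With equal slopes the shortfall is 0.23 to 0.38 points, well under the design standard error of 0.94. The larger shortfalls need a steeper drop-out slope on placebo. The documents also do not establish how well 6-month LVEF predicts the 24-month value; that is primary Aim 2.

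**The trigger concerns data that are not MAR, while most scenarios are MAR once the 6-month LVEF is modelled.** This stands in part. In scenario D the 6-month value moves the bias only from −1.74 to −1.43.

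**The 6-month scan can be missing in patients still on study (section 7.2), and many who stop study drug or start a statin stay in follow-up (sections 5.6.1 and 7.9).** Both are true, and both bear on how the fix is built.

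**The ratio weights as written are not the weights tested in step 3.** A drop-out-to-completer ratio represents only the drop-outs. Used literally, with baseline and arm, it gave biases from −1.33 to +1.97 across the scenarios run, including one driven purely by a baseline covariate. That is a separate matter, but the fix should not inherit it.

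**Conclusion.** The concern holds in a limited form. The described fallback does not remove bias from drop-out related to post-baseline events beyond what baseline and arm explain, although such missingness is one of its triggers. It also leaves out the 6-month LVEF that the mixed model uses.

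Under the assumptions in step 2, a true effect of 2.64 is estimated at about 1.4 to 2.4, and somewhat closer to the truth if other baseline covariates are prognostic. Including the 6-month LVEF gives about 2.64. The bias vanishes when slopes and drop-out rates are equal between arms. These figures show direction and range and are not a forecast. The point affects a conditional analysis of the primary endpoint; it does not undermine the primary ANCOVA specification or the sample size. It is worth correcting because the data are already collected.

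**What to change.** Replace the example in section 12.4 with a specified method, to apply if the fallback is used:

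1. Build retention weights in two steps. First model retention to month 6 given arm and baseline characteristics. Then model retention from month 6 to the final MRI given arm, baseline, 6-month LVEF where obtained, and events recorded before drop-out (toxicity, study-drug stop, open-label statin). Weight completers by the product of the inverse retention probabilities, not by the drop-out-to-completer ratio.
2. Alternatively, use multiple imputation that includes the same variables. This also handles patients without a 6-month scan.
3. Add a delta-adjusted sensitivity analysis for data not MAR, because 6-month data only partly correct drop-out that depends on the unseen 24-month LVEF.

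The cost is a few lines in the SAP, slightly more programming and somewhat more variable weights. With about 78 drop-outs expected, the list of predictors should be short and fixed in advance. No new data collection is needed.

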12.6. Power and Sample Size considerations for the primary hypothesis

For the primary hypothesis, sample size and power calculations can be made based on direct comparisons between the expected changes in outcome means in the different treatment groups. These calculations need to account for the proportion of the variance in the primary efficacy of outcome (LVEF) explained by the other terms in the model (i.e., baseline values). To adjust for the proportion of variance explained by the baseline measurement when estimating the variance for the follow-up outcome measure, we used the formula [$V_{\text{follow-up adjusted for baseline covariates}} = V_{\text{follow-up}} (1-r^2)$], where r^2 is the square of the correlation between the baseline and follow-up measure. Our primary efficacy analysis is based on comparing the change in LVEF levels from baseline to 24 – 27 months, and r above is the correlation between these two measurements. These power calculations may be conservative, since intermediate assessments of LVEF at 6 months are not included. In other words, the mixed models approach (described in the additional analyses) would likely provide greater power than the ANCOVA model used here, but further assumptions concerning the covariance structure to be used and correlation among intermediate measures would need to be made. Thus, we believe that the power described by the simpler method (ANCOVA) is adequate to address our hypotheses and is expected to be conservative.

The following formula was used to describe the minimum detectable difference for the LVEF between the statin and placebo groups:

$$\text{Detectable difference} = \sigma \frac{\sqrt{2(1-r^2)}(Z_{1-\alpha/2} + Z_{1-\beta})}{\sqrt{n}}$$

In the above, r^2 is the percent of the variance of the follow-up outcome explained by the baseline measurement (LVEF), $Z_{1-\alpha/2}$ is the value from the standard normal distribution corresponding to the alpha level chosen (1.96, which corresponds to alpha=0.05 [two sided]), $Z_{1-\beta}$ is the value from the standard normal distribution that corresponds to the power chosen for the study (here 80% and 90%), and $n=100$ corresponds to the total number of patients studied for the statin group. We chose this sample size (100 per group) for power calculations to allow for up to 78 patients out of the 278 accrued to potentially drop-out. Note that this will somewhat conservative for the mixed models as those with partial data will also provide information. Based on preliminary data examining LVEF levels in comparable patients measured over a 6-month period we found that the standard deviation was approximately 7.7 and the correlation between baseline and 6-months was 0.5. Since we do not know what the correlation will be after 2 years, Table 5 depicts detectable differences for different correlations and power values. In addition, we show detectable differences for key secondary variables for which we have preliminary data (LVEDV, LVESV, and PWV).

Thus, for example, we have 80% power to detect a difference of 2.6% in LVEF between groups if the correlation between the baseline and 24-month LVEF is 0.5. In preliminary observational data, we saw a difference in LVEF between statin users vs. those who were not of 2.5% at 6 months. Thus, effect sizes of the magnitude in Table 5 are plausible and clinically meaningful. 2-6 ml increases in LVESV, or 3-5% drops in LVEF (from a normal resting LVEF) have been associated with adverse CV prognoses in a recent large trial of patients with HF and a preserved resting LVEF.⁸¹ In 483 hypertensive patients aged 50±13 years, aortic PWV measures of 11 m/s were associated with odds ratio of 2.14 for cardiac events ($p<0.0001$).⁸² Other studies that have initiated generic therapies such as ACE inhibitors or beta blockers with antioxidant properties have shown a reduced occurrence of CV events in cancer survivors.⁸³ Importantly however, it remains to be seen whether early initiation of statin therapy reduces the onset of subclinical CV disease in patients with breast cancer or lymphoma.

Outcome	Estimated SD	80% Power			90% Power		
		Correlation between baseline and 2-yr measure					
		0.4	0.5	0.6	0.4	0.5	0.6
LVEF (%)	7.7	2.79	2.64	2.44	3.23	3.06	2.82
LV-EDV (ml)	33.1	12.0	11.4	10.5	13.9	13.1	12.1
LV-ESV (ml)	19.7	7.1	6.8	6.2	8.3	7.8	7.2
PWV (m/sec)	3.7	1.34	1.27	1.2	1.6	1.5	1.4

12.7. Reporting and Exclusions

We will measure the level of compliance in randomized patients. If a patient drops out of the study early due to an adverse event that may be related to statin use, they will be non-compliant for subsequent treatment, and thus still inform the primary endpoint for our analyses, and their outcome will be considered as “non-compliant”. For patients who drop out early due to a non-statin related adverse event or die during the study we will analyze them in the following ways.

First we will conservatively assume that all drop-outs/deaths are non-compliant. Since there is a placebo group in this study we can assume that the rates would be similar between groups and still allow a comparison of compliance rates between groups. Next, we will consider two forms of imputation for secondary analyses. The first will use early compliance data (if available) to determine a compliance rate and that value will be carried forward to the end (i.e., Last observation carried forward) and the second would be to use a multiple imputation procedure to impute final compliance rates for participants based on modeling the compliance rates for those with complete data.

12.8. Evaluation of Toxicity

All participants will be evaluable for toxicity from the time of their first dose of atorvastatin.

12.9. Evaluation of Response

All participants will be assessed for compliance once they are randomized to treatment and receive at least one dose of treatment. The primary analysis will consist of all randomized patients who receive at least one dose of study drug. Secondary analyses will consist of patients who either complete the trial (with $\geq 75\%$ compliance) or who drop out for adverse events that are related to the use of statins. Patients who drop out for non-related adverse events or die for reasons not related to statin use will be removed from the secondary analysis. Adverse events described by the Data Safety Monitoring Committee as related to statin use will be differentiated so as to render decisions regarding study drug compliance.

